5.4 Subject Enrollment

A patient is considered enrolled in the clinical investigation from the moment the patient provides written informed consent, has been confirmed to meet all inclusion criteria and none of the exclusion criteria, and eligibility has been confirmed by the medical monitor.

This confidential document is the property of Abbott and shall not be reproduced, distributed, disclosed or used without the express written consent of Abbott

Clinical Investigation Plan

Any subject enrolled into the clinical investigation who is later found not to meet all eligibility criteria, will be evaluated by the study team. If the deviation is found to violate the scientific integrity of the study or unduly influence the study aims, the subject will be withdrawn from the study. Otherwise, the subject will continue in the study and be included in the analysis population.

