5.5 Subject Deregistration

There will be no subject deregistration in this clinical investigation. If a subject was randomized and registered in the clinical investigation, the subject will be included in the analysis populations defined in Section 8.1.

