5.6 Subject Withdrawal and Discontinuation

Each subject meeting all general and screening eligibility criteria shall remain in the clinical investigation until completion of the required follow-up period; however, a subject's participation in any clinical investigation is voluntary and the subject has the right to withdraw at any time without penalty or loss of benefit. Conceivable reasons for discontinuation may include, but not be limited to, the following:

- Subject death
- Subject voluntary withdrawal
- Subject lost-to follow-up as described below
- Subject's follow-up is terminated according to Section 3.3
- Subject's neurostimulation system has been explanted
- Subject becomes pregnant
- Subject fails to comply with the protocol requirements

Sites must notify the Sponsor of the reason(s) for subject discontinuation. Investigators must also report this to their respective IRB/EC as defined by their institution's procedure(s).

No additional follow-up is required or data recorded from subjects once withdrawn from the clinical investigation, except for the status (deceased/alive).

However, if a subject withdraws from the investigation due to problems related to the safety or performance of the study device, the investigator shall ask for the subject's permission to follow his/her status/condition outside of the clinical investigation.

In case of subject withdrawal of consent, the site should make attempts to schedule the subject for a final clinical investigation visit. At this final follow-up visit, the subject will undergo the following assessments:

- Review of adverse events
- Administration of patient reported outcomes

Lost-to-Follow-up

If the subject misses two consecutive scheduled follow-up time points and the attempts at contacting the subject detailed below are unsuccessful, then the subject is considered lost-to-follow-up. Site personnel shall make all reasonable efforts to locate and communicate with the subject (and document these efforts in the source documents), including the following, at each contact time point:

This confidential document is the property of Abbott and shall not be reproduced, distributed, disclosed or used without the express written consent of Abbott

Clinical Investigation Plan

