6.3 Randomization

After enrollment has been completed, subjects will be randomized (3:2 ratio) to either the SCS arm or the CMM arm. Randomization will be stratified by site.

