2.3 Endpoint Analysis

2.3.1 Primary Endpoint

The primary effectiveness endpoint is the difference in response rates between groups at 6 months. A subject is considered a responder for the primary endpoint if the following criterion is met:

Improvement in pain, defined as a $\geq 50\%$ decrease on NRS.

2.3.1.1 The Hypothesis Test:

$$H_0: P_{SCS} = P_{CMM}$$

$$H_a: P_{SCS} \neq P_{CMM}$$

P_{SCS} and P_{CMM} denote the response rate at 6 months for SCS and CMM groups, respectively.

The ITT population defined in Section 2.1 will be used as the primary analysis. Trial failures (defined as having $< 50\%$ decrease in pain on the NRS from baseline to the end of the trialing, and who withdrew from the study per CIP), will be counted as non-responders in this analysis. All other subjects must complete their 6-month visit and have available primary endpoint data to be included in the primary analysis.

The response rates between the two groups will be compared using a two-sided Z-test with unpooled variance at the significance level of 0.05.

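### The protocol's rule for withdrawing ineligible subjects is not limited to the period before randomisation, and it conflicts with the rule that every randomised subject is analysed

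*Protocol*

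**What the plan says.** Protocol section 5.4 sets the rule for ineligibility discovered late: "Any subject enrolled into the clinical investigation who is later found not to meet all eligibility criteria, will be evaluated by the study team". Then: "If the deviation is found to violate the scientific integrity of the study or unduly influence the study aims, the subject will be withdrawn". It closes: "Otherwise, the subject will continue in the study and be included in the analysis population". The study team is not defined, no objective test is given for the criterion, and there is no time limit.

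Protocol section 6.3 puts randomisation after enrolment: "After enrollment has been completed, subjects will be randomized (3:2 ratio) to either the SCS arm or the CMM arm". Enrolled subjects therefore include randomised ones.

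Protocol section 5.5 rules out deregistration: "If a subject was randomized and registered in the clinical investigation, the subject will be included in the analysis populations defined in Section 8.1". Section 8.1 of the protocol is redacted, but SAP section 2.1 defines ITT as all randomised subjects and makes it the primary population for the primary endpoint.

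On data after withdrawal, protocol section 5.6 says: "No additional follow-up is required or data recorded from subjects once withdrawn from the clinical investigation", with vital status the only exception. The final visit with patient-reported outcomes in that section is described for withdrawal of consent.

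SAP section 2.3.1.1 counts SCS trial failures as non-responders. For everyone else: "All other subjects must complete their 6-month visit and have available primary endpoint data to be included in the primary analysis".

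SAP section 1.6 states that subjects, site personnel and some sponsor personnel know the assignment. Sponsor statisticians are kept from data that join outcomes to assignment until the primary analysis.

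**The concern.** Read together, these rules permit a post-randomisation exclusion from the primary comparison on a discretionary criterion worded in terms of the study's aims. The trial is open to site and some sponsor personnel, and no outcome-blind review of the decision is specified. Several exclusion criteria in protocol section 5.3.3 are themselves judgements that could be revisited later, such as items 17, 18 and 20.

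If such withdrawals were related to arm and outcome, the comparison would lose part of the protection of randomisation, in favour of either arm. There is also a practical problem: section 5.4 implies exclusion where section 5.5 requires inclusion, so two analysts could arrive at different primary denominators.

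**Working it through.** **1. Path of one subject through the rules.** Take a subject randomised, then found ineligible at month 2 and withdrawn under section 5.4.
- Section 5.4: by implication, not in the analysis population.
- Section 5.5 and SAP 2.1: in the analysis populations, including ITT.
- Section 5.6: no 6-month NRS need be recorded.
- SAP 2.3.1.1: unless a trial failure, the subject is left out of numerator and denominator of the primary test.
- SAP 2.3.1.2 and 2.9: the outcome is imputed, in a sensitivity analysis only.

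The loss arises from section 5.6 combined with the available-data rule. It affects subjects withdrawn after randomisation and before the 6-month visit.

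**2. The plan's power figure (SAP 2.4).** Inputs: 200 randomised in Phase I, 25% attrition, 3:2 allocation, response 45% v 20%, two-sided alpha 0.05, unpooled Z-test.
- Evaluable: 200 × 0.75 = 150, split 90 SCS and 60 CMM.
- SE = √(0.45×0.55/90 + 0.20×0.80/60) = 0.0736.
- Power = Φ(0.25/0.0736 − 1.96) = Φ(1.44) = 92.5%. Exact binomial enumeration gives 91.5%.

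This agrees with the stated 90% or more. If 10 further subjects were lost in proportion by arm and unrelated to outcome (84 v 56), power would be 90.7%. The issue is therefore bias and not power.

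**3. Worst-case bias.** The documents give no number of ineligibility withdrawals, so k is an assumption, and every removal is taken to be an SCS non-responder. With true rates equal, x ~ Bin(90, p) and y ~ Bin(60, p). I replace x/90 by x/(90−k) and sum the probability that the unpooled Z exceeds 1.96 (nominal 2.5%).

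| Common rate | k=0 | k=2 | k=5 |
|---|---|---|---|
| 20% | 2.9% | 4.0% | 4.4% |
| 45% | 2.8% | 3.8% | 5.8% |

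The excess over 2.5% at k=0 comes from the unpooled Z-test itself. At 20%, the total two-sided error goes from 5.2% (2.9% + 2.3%) to 5.8% (4.0% + 1.9%) with two removed.

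**4. Single data sets,** Z = (a − b)/√(a(1−a)/n₁ + b(1−b)/n₂), where a and b are the observed response rates:
- 34/90 v 14/60: 0.1444/0.0748 = 1.93, p = 0.053. One SCS non-responder removed, 34/89: 0.1487/0.0751 = 1.98, p = 0.048.
- 32/90 v 13/60: p = 0.058. Two removed, 32/88: p = 0.047.
- Near the planned rates, 40/90 v 12/60: 0.2444/0.0735 = 3.32, p = 0.0009. With two removed, 40/88: p = 0.0006.

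Removals matter only when the result is close to the boundary.

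**The case against.** The strongest reply is that no ITT claim is broken. Nothing in section 5.4 takes a randomised subject out of the ITT set; the outcome is missing, and the available-data rule treats it like any other missing outcome. That is right as to mechanism. It does not remove the clash between the closing sentence of section 5.4 and section 5.5, and the subject is still absent from the test that decides success.

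A second reply is that section 5.4 sits under the enrolment heading and may be meant only for subjects not yet randomised. That would reconcile it with section 5.5, but the text covers any enrolled subject and sets no such limit.

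A third points to safeguards. An independent medical monitor confirms eligibility before a patient counts as enrolled, deviations are recorded and summarised, early-termination reasons are reported, and multiple imputation restores all randomised subjects. These should keep cases few and visible. They do not change the primary analysis.

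A reader might go further and infer that an unblinded team will remove subjects according to how they are doing. The documents do not support that: membership of the study team is not stated, and nothing says it sees outcomes. What they do show is that the decision is not required to be blind to arm or outcome.

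**Conclusion.** The conflict between protocol section 5.4 on one side and section 5.5 and SAP 2.1 on the other is real and should be resolved. As written, the plan permits a discretionary exclusion from the primary test after randomisation and before month 6.

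Its likely size is small. Under one-directional removal of SCS non-responders, two to five removals raise the chance of a false SCS win from about 3% to between 4% and 6%, and one or two can tip a borderline result. These are illustrations with an assumed k, not estimates for this trial. At the planned effect the conclusion would not change, and neither the power statement nor the sample size needs revision. It would be too strong to say that the plan abandons ITT or that selective removal is expected. The defensible statement is that the rule leaves an avoidable route to it.

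**What to change.** - **Protocol 5.4:** limit withdrawal from the study for ineligibility to the period before randomisation. After randomisation, log the deviation and keep the subject in the ITT analysis.
- **Protocol 5.6:** amend to match, so that the 6-month NRS is still collected, with the subject's consent, whether or not study treatment continues.
- **SAP:** show exclusion of ineligible subjects only as a sensitivity analysis, with the list fixed by reviewers who have no access to outcomes.

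The cost is short edits in these three places and slight dilution of the treatment comparison from a few ineligible subjects.

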5.4.1 Enrollment of Medicare Beneficiaries

This clinical investigation will enroll Medicare beneficiaries and therefore conforms to all standards of Medicare coverage requirements. The Risks and Benefits section describes how all enrolled subjects, including Medicare beneficiaries, may be affected by the device under investigation.

A portion of the subjects enrolled in the clinical investigation display characteristics consistent with the Medicare population based on age. The clinical investigation results will be analyzed by age (< 65 years and ≥ 65 years) and compared to ensure that the outcomes are similar between the Medicare and non-Medicare populations.

5.4.2 Historically Under-Represented Demographic Subgroups

The Sponsor intends to implement FDA's guidance on sex-specific data in medical device clinical investigations to ensure adequate representation of women and other traditionally under-represented demographic subgroups in this clinical investigation. As noted in the guidance, some barriers to participation of women and ethnic minorities in clinical investigations have traditionally been:

- Lack of understanding about main obstacles to participation of such subgroups in clinical research
- Inclusion/exclusion criteria potentially not needed to define the clinical investigation population may unintentionally exclude specific subgroups
- Under diagnosis of disease etiologies and pathophysiology leading to under referral of demographic subgroups
- Avoidance of specific subgroups by investigators and Sponsors due to the perception that it takes more time and resources to recruit them
- Fear of fetal consequences (for female participants)
- Family responsibilities limiting women's ability to commit time for follow-up requirements

The Sponsor will take the following steps to ensure adequate representation of women and racial or ethnic minorities in this clinical investigation:

- The Sponsor will provide training to investigational site personnel to ensure adequate representation of these demographic subgroups
- The Sponsor will regularly review enrollment data to investigate whether there is under-representation of these demographic subgroups
- The Sponsor will regularly review withdrawal rates for under-represented subgroups and compare these rates with that in the overall clinical investigation population
- As appropriate and necessary, the Sponsor will retrain sites on the importance of recruiting and retaining subjects in the clinical investigation
- The Sponsor will approach sites without bias or consideration for specific demographic subgroups

This confidential document is the property of Abbott and shall not be reproduced, distributed, disclosed or used without the express written consent of Abbott

Clinical Investigation Plan

- The Sponsor will have informed consent materials in alternative languages and will work with sites and IRBs/ECs on recruitment materials

5.5 Subject Deregistration

There will be no subject deregistration in this clinical investigation. If a subject was randomized and registered in the clinical investigation, the subject will be included in the analysis populations defined in Section 8.1.

5.6 Subject Withdrawal and Discontinuation

Each subject meeting all general and screening eligibility criteria shall remain in the clinical investigation until completion of the required follow-up period; however, a subject's participation in any clinical investigation is voluntary and the subject has the right to withdraw at any time without penalty or loss of benefit. Conceivable reasons for discontinuation may include, but not be limited to, the following:

- Subject death
- Subject voluntary withdrawal
- Subject lost-to follow-up as described below
- Subject's follow-up is terminated according to Section 3.3
- Subject's neurostimulation system has been explanted
- Subject becomes pregnant
- Subject fails to comply with the protocol requirements

Sites must notify the Sponsor of the reason(s) for subject discontinuation. Investigators must also report this to their respective IRB/EC as defined by their institution's procedure(s).

No additional follow-up is required or data recorded from subjects once withdrawn from the clinical investigation, except for the status (deceased/alive).

However, if a subject withdraws from the investigation due to problems related to the safety or performance of the study device, the investigator shall ask for the subject's permission to follow his/her status/condition outside of the clinical investigation.

In case of subject withdrawal of consent, the site should make attempts to schedule the subject for a final clinical investigation visit. At this final follow-up visit, the subject will undergo the following assessments:

- Review of adverse events
- Administration of patient reported outcomes

Lost-to-Follow-up

If the subject misses two consecutive scheduled follow-up time points and the attempts at contacting the subject detailed below are unsuccessful, then the subject is considered lost-to-follow-up. Site personnel shall make all reasonable efforts to locate and communicate with the subject (and document these efforts in the source documents), including the following, at each contact time point:

This confidential document is the property of Abbott and shall not be reproduced, distributed, disclosed or used without the express written consent of Abbott

Clinical Investigation Plan

- A minimum of two telephone calls on different days over the specified follow-up windows to contact the subject should be recorded in the source documentation, including date, time and initials of site personnel trying to make contact.
- If these attempts are unsuccessful, the site should send a letter (certified if applicable) to the subject.
- If a subject misses one or more non-consecutive follow-up contact time points, it will be considered a missed visit. The subject may then return for subsequent visits. If the subject misses two consecutive time points and the above-mentioned attempts at communicating with the subject are unsuccessful, the subject will be considered lost-to-follow-up.

Note: Telephone contact with General Practitioner or relative without the presence of the subject or indirect documentation obtained via discharge letters will not be considered as subject contact.

Clinical Investigation Plan

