6.6.4 Crossover

Crossover prior to the study primary endpoint is not allowed. To ensure valid analysis of all endpoints, investigators and coordinators must make concerted efforts to prevent crossover from CMM to SCS prior to completing the 6-month visit. If a subject is unwilling to complete the assigned treatment, they should be withdrawn. Upon completion of the 6-month primary endpoint visit, a subject is allowed to crossover to the other arm. The permanent implant must occur prior to the [REDACTED] follow up visit.

Clinical Investigation Plan

Subjects crossing over to the SCS arm will follow the trial and permanent SCS procedures as part of standard of care. Upon receiving a permanent implant, subjects will continue to participate in the study according to Section 6.6. The follow-up timeline will not be reset; the subject will continue with the follow-up schedule. Subjects are not allowed to crossover more than once.

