7.1.2 Serious Adverse Event

If the AE meets any of the criteria below, it is regarded as a serious adverse event (SAE).

- a) Led to a death
- b) Led to a serious deterioration in health of the subject, that either resulted in
 1. a life-threatening illness or injury, or
 2. a permanent impairment of a body structure or a body function, or
 3. in-patient hospitalization or prolongation of existing hospitalization, or
 4. medical or surgical intervention to prevent life threatening illness or injury or permanent impairment to a body structure or a body function
 5. chronic disease
- c) Led to fetal distress, fetal death or a congenital abnormality or birth defect

Note: A planned hospitalization for a pre-existing condition, or a procedure required by the CIP without a serious deterioration in health, is not considered to be an SAE.

Clinical Investigation Plan

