7.3 Adverse Events

7.3.1 Adverse Event Reporting

General AE Reporting

Safety surveillance and reporting starts as soon as the patient is enrolled in the clinical investigation. Safety surveillance and reporting will continue until sites perform the last follow-up visit, the subject is deceased, the subject concludes participation in the clinical investigation, or the subject withdraws from the clinical investigation. Sites will collect all adverse event data including deaths per protocol throughout the period defined above and will report these events to the Sponsor on a CRF. Sites should update additional information regarding an adverse event on the appropriate CRF.

Unchanged, chronic, non-worsening or pre-existing conditions are not AEs and should not be reported.

The Sponsor will provide an offline form to allow the investigator to report SAEs in the event the entry cannot be made in the EDC. This does not replace the EDC reporting system. Sites must still enter all information in the EDC system as soon as feasible.

SAE Reporting

The investigator must report all SAEs to the Sponsor as soon as possible but no later than outlined below.

Clinical Site	Reporting timelines
All Sites	Sites must report SAEs to the Sponsor no later than 3 calendar days from the day the site personnel became aware of the event or as per the investigative site's local requirements, if the requirement is more stringent than those outlined.

Clinical Investigation Plan

Sites must record the date the site staff became aware that the event met the criteria of an SAE in the source document. The Investigator will further report the SAE to the local IRB/EC according to the institution's IRB/EC reporting requirements.

Reportable events to the sponsor are considered:

- All adverse events related to the SCS device and/or SCS procedure regardless of seriousness criteria.
- All serious adverse events including deaths

Refer to the specific device manuals for adverse events associated with the use of SCS systems.

Device deficiencies (DD) are not collected on a DD form in this study. Sites should report all device deficiencies/malfunctions to the Sponsor's Customer Service Department.

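### Once a subject leaves the study, adverse event recording stops, so the later course of device and procedure complications after explant or a failed trial can be lost from the safety results

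*Protocol*

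**What the plan says.** **Routes out of the study.** CIP 5.6 begins from the default that subjects stay in until follow-up is complete. It then introduces a list with the words "Conceivable reasons for discontinuation may include, but not be limited to, the following". The list includes the case where the "neurostimulation system has been explanted", and pregnancy. A failed stimulation trial is not on it. CIP 6.5 makes trial success a condition for the permanent implant, and CIP 6.5.3 records withdrawal where it applies. SAP 2.3.1.1, however, defines trial failures as subjects below the 50% threshold "and who withdrew from the study per CIP".

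**What happens at exit.** CIP 5.6: "No additional follow-up is required or data recorded from subjects once withdrawn from the clinical investigation, except for the status (deceased/alive"). CIP 7.3.1 runs safety surveillance until, among other end points, "the subject concludes participation in the clinical investigation, or the subject withdraws from the clinical investigation".

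**Safeguards in CIP 5.6.** If the withdrawal is for device safety or performance, the investigator asks permission to follow the subject's "status/condition outside of the clinical investigation". If consent is withdrawn, the site should try to arrange a last visit with an adverse event review and questionnaires.

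**Where the data are used.** Serious device-related adverse events are a descriptive endpoint (CIP 4.3, SAP 3.5.1). SAP 3.2 reports event counts, the percentage of subjects with events, and rates per subject-year.

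**The concern.** Stopping treatment and stopping safety observation are separate decisions, but the plan joins them at the point of exit. An explant or a failed trial can itself follow from how the device performed. If such a subject leaves, observation ends for a reason linked to the outcome being measured, which is informative censoring of the safety data.

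Two kinds of information are at risk: complications that first appear after the leads or system are removed, and the resolution or outcome of events still open on the day of exit. Pregnancy raises a related gap. CIP 7.1.2 counts as serious an event that "Led to fetal distress, fetal death or a congenital abnormality or birth defect", yet a pregnant subject may be discontinued, and no collection of pregnancy outcome is described after that.

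The primary NRS comparison is not at stake. What is at stake is whether the device-safety results are complete, in a trial whose Steering Committee may recommend stopping because of a higher frequency of device effects (CIP 3.3).

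**Working it through.** The plan gives no figure for this point, so the check is mainly a comparison of texts.

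**Step 1. Is exit required or permitted?**
- Explant and pregnancy: permitted. The CIP 5.6 list is of possible reasons, set against a default of remaining in the study.
- Failed trial: the CIP text available has no exit rule. SAP 2.3.1.1 refers to withdrawal under the CIP. The CIP also describes no follow-up path for these subjects: CIP 6.5.4 takes forward those with at least 50% improvement who wish to continue, and visits in CIP 6.6.1 and 6.6.3 are timed from randomization or permanent implantation. The two documents need reconciling.

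**Step 2. What is recorded after exit?**

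| Situation at exit | Review at exit stated? | Recording in study data afterwards |
|---|---|---|
| Explant | No, unless consent is withdrawn | Vital status only; follow-up outside the study, by permission, if withdrawal is for device safety or performance |
| Failed trial | End of Trial visit records AEs and SAEs (CIP 6.5.3) | Vital status only, if the subject withdraws; same outside follow-up if device-related |
| Pregnancy | No, unless consent is withdrawn | Vital status only |
| Withdrawal of consent | Yes, attempted final visit | Vital status only |

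No row has a stated route by which a later event, or the outcome of an open one, reaches the study data.

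**Step 3. What does this do to the summaries?** SAP 3.2 includes all subjects who completed enrollment.
- Percentage of subjects with an event: an exited subject stays in the denominator, so a first event missed after exit can only lower the percentage.
- Rate per subject-year: if person-time is counted to exit, both the later time and the later events drop out. The rate is too low if the event rate after exit would have exceeded the in-study rate, and too high if it would have been below it. The documents do not settle the direction.
- Outcome and resolution of events open at exit: not recorded in either case.

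**Step 4. Illustrative scale.** Inputs: about 200 Phase I subjects and 3:2 allocation (SAP 2.4); two years of follow-up (SAP 1.3). The trial-failure rate is an assumption, because the documents give none.
- SCS subjects in Phase I: 200 × 3/5 = 120.
- Planned SCS follow-up: 120 × 2 = 240 subject-years.

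| Assumed trial failure | Subjects, if all exit | Subject-years unobserved (upper bound) | Share of 240 |
|---|---|---|---|
| 10% | 120 × 0.10 = 12 | 12 × 2 = 24 | 10% |
| 20% | 120 × 0.20 = 24 | 24 × 2 = 48 | 20% |
| 30% | 120 × 0.30 = 36 | 36 × 2 = 72 | 30% |

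The subject-years are upper bounds because some time passes before exit. Explants would add to the count, but no rate is given and none is assumed here.

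**The case against.** The best reply is that the plan already captures most of what matters. The event that leads to exit is reportable before exit. Unscheduled visits document adverse events (CIP 6.6.5), and sites update event information on the CRF (CIP 7.3.1). Source records must hold adverse events with their resolution (CIP 11.3), and CIP 15.5 says device-related events will be reported and monitored. The Clinical Events Committee adjudicates device- and procedure-related events (CIP 3.2). The devices are marketed and under vigilance reporting, with a separate Safety Plan (CIP Appendix XIII) that was not available. Safety is descriptive, success rests on NRS response alone, and rates per subject-year allow for unequal follow-up.

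Much of this stands, and it limits the consequence. It does not close the gap. CIP 5.6 still stops recording at exit, no stated route carries vigilance reports or outside follow-up into the SAP 3.2 tables, and subject-year rates do not correct for exit that depends on the outcome.

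A reader might also infer several stronger points that the documents do not support:
- **That exit is compulsory.** CIP 5.6 only permits it for explant and pregnancy. For failed trials the statement is in the SAP, and the CIP flow chart, Schedule of Events and analysis-population text cannot be seen.
- **That CIP 5.6 contradicts CIP 6.6.4.** After the 6-month visit "a subject is allowed to crossover to the other arm", but 6.6.4 does not require the system to be removed on moving to CMM, and 5.6 does not require exit if it is. The separate crossover instructions were not available.
- **That only device recipients lose follow-up.** Pregnancy applies to both arms, and 6.6.4 has subjects who will not complete their assigned treatment withdrawn, which reaches CMM subjects too.
- **That every explant reflects an adverse event.** It need not.
- **That a trial-failure rate can be read from SAP 2.4.** Comparing about 80 SCS subjects in the PTE planning figure with 120 × 0.75 = 90 evaluable suggests 10/90 = 11%; against all 120 randomized it is 10/120 = 8%. The 80 is a rounded planning number, and non-implantation also covers subjects who choose not to proceed. Neither figure is a failure rate.

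**Conclusion.** The point holds as a gap in safety data collection, not as a mandatory loss of subjects. Exit is permitted after explant or pregnancy and is taken for granted by the SAP after a failed trial. When it happens, in-study adverse event recording ends, and neither safeguard returns later information to the study data. For explant and failed trial, exit depends on the device outcome, so censoring may be informative.

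The size cannot be derived from the documents. The range of 12 to 36 Phase I SCS subjects rests on an assumed 10% to 30% failure rate and on all of them leaving. It counts subjects whose observation would be cut short, not missed events. The primary endpoint and the success criterion are unaffected. The change is worth making because it is cheap and bears directly on the completeness of the device-safety results.

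**What to change.** Amend CIP 5.6 and 7.3.1 so that, unless the subject withdraws consent:

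1. any SAE or device- or procedure-related adverse event open at exit is recorded in the EDC until it resolves or the planned end of follow-up;
2. the existing final adverse event review applies to every reason for discontinuation, including explant, failed trial and pregnancy, by telephone if needed (CIP 6.6.3 already provides a format);
3. follow-up of device problems, with the subject's permission, is entered in the study data.

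Reconcile CIP 5.6 and 6.5 with SAP 2.3.1.1 on whether failed-trial subjects leave the study.

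The cost is a protocol and consent amendment and a small number of extra contacts. No treatment, visit schedule for continuing subjects, or efficacy analysis changes.
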